6.2.1.3. Adverse Events of Special Interest

An AESI (serious or non-serious) is one of scientific and medical concern for which ongoing monitoring and rapid communication by the investigator to the sponsor can be appropriate. Adverse events of special interest for this study include liver tests that meet the criteria for potential drug-induced liver injury (DILI), in accordance with the US Food and Drug Administration (FDA) “Guidance for Industry-Drug-Induced Liver Injury: Premarketing Clinical Evaluation.”

Liver Tests and Stopping Criteria

The following 3 laboratory value criteria must be met for potential DILI, or “Hy’s Law”:

- An elevated alanine transaminase or aspartate transaminase laboratory value that is $\geq 3 \times$ ULN
- An elevated total bilirubin laboratory value that is $\geq 2 \times$ ULN
- An alkaline phosphatase laboratory value that is $< 2 \times$ ULN

Study drug should be discontinued for subjects who meet the laboratory criteria for potential DILI as a result of within-protocol specific testing or unscheduled testing. This AESI must be reported to the sponsor within 24 hours of awareness. Further safety steps should be taken to closely observe and follow-up the event until resolution. These steps include, but are not limited to:

- Making every reasonable attempt to have the subject return to the clinic within 24 hours for repeat liver tests
- Obtaining a more detailed history of symptoms and prior or concurrent disease, concomitant medication use, alcohol use, recreational drug use, and special diets
- Repeating liver enzyme and serum bilirubin tests twice weekly. Frequency of retesting can decrease to once a week or less if abnormalities stabilize and the subject is asymptomatic
- Obtaining viral hepatitis serology
- Considering liver imaging and/or hepatology consultation

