### **9.2.2. Serum Chemistry**

The following laboratory tests will be included: glucose, sodium, potassium, calcium, inorganic phosphate, total protein, albumin, blood urea nitrogen, creatinine, total bilirubin, alkaline phosphatase (ALP), aspartate aminotransferase (AST), alanine aminotransferase (ALT), gamma-glutamyl transferase, and creatinine phosphokinase.

Summary tables presenting observed values and changes from baseline will be presented for the following serum chemistry tests: direct bilirubin, alkaline phosphatase, aspartate aminotransferase, alanine aminotransferase, and gamma-glutamyltransferase. Changes from baseline to each scheduled post-baseline visit will be presented. All chemistry data by subject will also be presented in a listing.

The clinical assessment of ‘Low’, ‘Normal’, or ‘High’ relative to the reference range will be summarized comparing the baseline results to the minimum and maximum values post-baseline in separate shift tables for those subjects with results at both baseline and post-baseline visits.

Results indicating liver-related abnormalities (i.e., ALT, AST, Total Bilirubin, and/or ALP) will be summarized separately. A newly notable laboratory abnormality is defined as an abnormality observed post baseline that meets the notable criteria in [Table 9-1](#) and that did not exist at baseline. Subjects can still meet the criteria for a newly notable laboratory abnormality if the baseline value is missing. The table below displays the general variables and thresholds of interest. Subjects are considered to have notable laboratory abnormalities if his/her response falls within the specified definitions at least once during the treatment period.

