**Table 9-1: Notable Criteria for Laboratory Data Abnormalities – Liver Function Tests**

Laboratory Variable	SI Units
AST	$\geq 3 \times \text{ULN}$
ALT	$\geq 3 \times \text{ULN}$
Total Bilirubin	$\geq 2 \times \text{ULN}$

A summary of liver tests that meet the criteria for potential drug induced liver injury (DILI) will be presented. A potential DILI or Hy's law case is defined as ALT or AST  $\geq 3 \times \text{ULN}$  and total bilirubin  $\geq 2 \times \text{ULN}$  and ALP  $\leq 2 \times \text{ULN}$ .

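### SAP 9.2.2 promises a separate liver summary that includes ALP but sets no ALP criterion, describes no combined summary above the DILI limit for ALP, and states that limit differently from the protocol

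*SAP*

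**What the plan says.** SAP 9.2.2 (Serum Chemistry) names four tests for a liver display of their own: "Results indicating liver-related abnormalities (i.e., ALT, AST, Total Bilirubin, and/or ALP) will be summarized separately". It then sets the rule for counting: "A newly notable laboratory abnormality is defined as an abnormality observed post baseline that meets the notable criteria in". The criteria are those of Table 9-1, and an abnormality already present before treatment does not count as new. The table, headed "Table 9-1: Notable Criteria for Laboratory Data Abnormalities – Liver Function Tests", has three rows: AST ≥3 × ULN, ALT ≥3 × ULN and total bilirubin ≥2 × ULN.

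Below the table is the one combined criterion: "A potential DILI or Hy's law case is defined as ALT or AST". The thresholds it sets are 3 × ULN or more for either transaminase, 2 × ULN or more for total bilirubin, and ALP ≤2 × ULN. SAP 9.1 refers to Section 9.2.2 for the liver criteria behind the adverse event of special interest (AESI).

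Protocol 6.2.1.3 sets out the same construct: "The following 3 laboratory value criteria must be met for potential DILI". Its third criterion is "An alkaline phosphatase laboratory value that is" strictly less than 2 × ULN. The protocol links meeting these criteria to discontinuing study drug.

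**The concern.** There are three distinct points.

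- **No ALP criterion.** The text commits to an ALP summary that its own rule cannot produce. A programmer would have to invent a threshold, or would leave ALP out, and a reader could take the absence of notable ALP results as a finding.
- **No combined summary above the ALP limit.** Raised transaminase with raised bilirubin is brought together in one display only when ALP is at or below 2 × ULN. Above that, no described summary shows that the two rises occurred in the same subject.
- **Two definitions of the AESI.** The SAP and the protocol do not use the same ALP limit, and SAP section 11, which records modifications from the protocol, covers only the interim analysis and the open-label analysis set.

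Potential DILI is the only AESI the protocol names, and safety is the primary objective of the open-label extension. Protocol 1.5 notes that hepatotoxicity has been seen with some other p38 MAPK inhibitors and that its applicability to losmapimod is unknown. The liver tables should therefore follow from an exact rule.

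**Working it through.** The plan states no figure to reproduce here. The check applies the written rules to one pattern: ALT or AST ≥3 × ULN and total bilirubin ≥2 × ULN, neither notable at baseline, with ALP varied.

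**Inputs**

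- Single-test rule: SAP Table 9-1 (AST, ALT, total bilirubin).
- SAP combined rule: ALT or AST ≥3 × ULN, total bilirubin ≥2 × ULN, ALP ≤2 × ULN (SAP 9.2.2).
- Protocol combined rule: the same, with ALP <2 × ULN (protocol 6.2.1.3).
- Shift rule: Low, Normal or High, baseline against post-baseline minimum and maximum (SAP 9.2.2).

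**Result**

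| ALP | DILI, SAP | DILI, protocol | ALT/AST and bilirubin flagged singly | ALP flagged as notable | ALP in shift table |
|---|---|---|---|---|---|
| 1.5 × ULN | yes | yes | yes | no | High |
| 2.0 × ULN | yes | no | yes | no | High |
| 2.5 × ULN | no | no | yes | no | High |

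Three things follow.

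1. The column for a notable ALP result is empty at every value, because Table 9-1 has no row that could fill it.
2. At 2.5 × ULN the subject leaves the combined criterion under both documents. The planned outputs contain one combined liver table (14.3.4.2.4) and one matching listing (16.2.8.2.2), both titled for DILI. Table 14.3.4.2.3 covers the notable results.
3. The two DILI definitions part only at exactly 2.0 × ULN, where the SAP counts a case that the protocol does not.

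**Where the values remain visible**

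- *By-visit summaries.* ALP, ALT and AST are in the observed-value and change-from-baseline table (14.3.4.2.1). SAP section 4 includes the maximum among the statistics for continuous variables, so the largest ALP and the largest ALP rise appear at each visit. The tests listed for this table include direct bilirubin but not total bilirubin.
- *Shift table* (14.3.4.2.2). It shows ALP as High but does not separate a small rise from a large one, and it does not link tests within a subject.
- *Chemistry listing* (16.2.8.2.1). All values are shown by subject, so coinciding rises can be read there.
- *Adverse events.* Protocol 6.2.2 requires clinically significant abnormal results to be recorded as AEs or SAEs, except those associated with the underlying disease and not judged more severe than expected. Such cases would reach the AE tables.

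**The case against.** The strongest defence is that little is hidden. Maxima and changes for ALP are tabulated by visit, the full listing shows each subject's tests, both are marked for the Safety Review Committee, and a clinically significant case would be recorded as an AE. The ALP ceiling in the combined criterion is the protocol's own construct, which the SAP tabulates. An extra row above the ceiling is promised nowhere. The mention of ALP might also be read as met by the DILI table. Finally, the table shells are in a separate document and may contain more ALP categories than the text describes.

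Most of this stands, and it rules out several stronger readings:

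- A reader might infer that liver injury with raised ALP is never shown. The displays listed above contradict that; what is missing is a threshold count and a combined summary.
- A reader might infer that the DILI definition excludes all raised ALP. It admits values above ULN up to its limit.
- A reader might infer that the differing inequality causes cases to be lost. At the single value where it matters, the SAP is the more inclusive document.
- A reader might turn the 0.9% liver-event frequency in protocol 1.5 into an expected number of missed cases. That figure covers all liver events in the losmapimod group of 11 repeat-dose studies in other patient populations, and the open-label analysis set is those who rolled over, not all 80 enrolled. It does not give the frequency of this pattern.

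Two parts of the defence do not succeed. In the DILI definition ALP enters only as a ceiling, so the DILI table does not count ALP abnormalities and does not meet the commitment to summarise them. And shells may add detail, but the SAP text should define the criterion they display.

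**Conclusion.** The point holds as a reporting defect of limited size.

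- As written, the number of notable ALP results is zero by construction, whatever the data.
- Subjects with ALT or AST ≥3 × ULN, total bilirubin ≥2 × ULN and ALP above 2 × ULN are in no described combined summary. Their individual results are still reported.
- The ≤ versus < conflict is a separate consistency error confined to exactly 2.0 × ULN. It still needs correcting, because it sits in the definition of the only named AESI and is undeclared.

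This rests on Table 9-1 having the three rows shown, with no sign of a redacted or broken row, and on the SAP text and output titles alone, since the shells could not be checked. No claim is made about how many such cases to expect, or about which ALP inequality is right.

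**What to change.** 1. Reconcile the ALP limit between SAP 9.2.2 and protocol 6.2.1.3, so that the AESI count, Table 14.3.4.2.4 and Listing 16.2.8.2.2 use one definition. The choice is left to the sponsor because the protocol ties this limit to discontinuing study drug.
2. Add an ALP criterion to Table 9-1 based on the reconciled limit, or remove ALP from the sentence in SAP 9.2.2.
3. Add to Table 14.3.4.2.4 a row for ALT or AST ≥3 × ULN with total bilirubin ≥2 × ULN regardless of ALP, split at the reconciled limit.

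The cost is wording and table rows. ALP is already in the serum chemistry panel (protocol 6.2.2), so no new data are needed. Items 2 and 3 change reporting only and touch neither stopping rules nor patient management.

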**Table 9-1: Notable Criteria for Laboratory Data Abnormalities – Liver Function Tests**

Laboratory Variable	SI Units
AST	$\geq 3 \times \text{ULN}$
ALT	$\geq 3 \times \text{ULN}$
Total Bilirubin	$\geq 2 \times \text{ULN}$

A summary of liver tests that meet the criteria for potential drug induced liver injury (DILI) will be presented. A potential DILI or Hy's law case is defined as ALT or AST  $\geq 3 \times \text{ULN}$  and total bilirubin  $\geq 2 \times \text{ULN}$  and ALP  $\leq 2 \times \text{ULN}$ .

### **9.2.3. Urinalysis**

The following urine laboratory tests will be included: leukocytes, blood, nitrite, protein, urobilinogen, bilirubin, pH, specific gravity, ketones, and glucose.

Summary tables presenting observed values and changes from baseline will be presented for the following urinalysis tests: glucose, blood and protein. Changes from baseline to each scheduled post-baseline visit will be presented.

All urinalysis data by subject will be presented in a listing.

## **9.3. Vital Sign Measurements**

Summary tables will be presented for vital sign data, including pulse rate, respiration rate, blood pressure, temperature, height, weight and BMI. BMI will be calculated based on the collected height and weight if missing. Observed results at each visit as well as the change from baseline to each post-dose assessment will also be presented. Results from both the

placebo-controlled treatment period and OLE will be summarized over time. All vital sign data by subject will also be presented in a listing.

#### **9.4. Physical Examination**

A table will summarize physical examination results. Status of a body system and any finding associated with the body system as normal, abnormal, or not done will be captured at screening and safety follow-up. Results from both the placebo-controlled treatment period and OLE will be summarized over time. Physical examination results for all subjects will also be presented in a listing.

#### **9.5. Electrocardiogram**

Subjects will have a standard 12-lead ECG performed during the study. Results from both the placebo-controlled treatment period and OLE will be summarized over time. Electrocardiogram data for all subjects will be presented in a listing.

Each subject's maximum on-treatment QTcF interval will be categorized as  $\leq 450$ ,  $> 450$  to  $\leq 480$ ,  $> 480$  to  $\leq 500$ , and  $> 500$  msec. The number and percentage of subjects in each category will be presented by treatment group. Each subject's maximum on-treatment change from baseline in QTcF interval will be categorized as  $< 0$ ,  $\geq 0$  to  $\leq 30$ ,  $> 30$  to  $\leq 60$ ,  $> 60$  msec. The number and percentage of subjects in each category will be presented by treatment group.

ECG data for all subjects will also be presented in a listing.

### **10. Pharmacokinetics**

By-subject listing of pharmacokinetic blood sample and muscle sample collection times as well as derived sampling time deviations will be provided. Losmapimod plasma and muscle concentrations will be summarized using descriptive statistics (n, mean, standard deviation, minimum, median, maximum, coefficient of variation) by scheduled time point. Concentrations that are below the limit of quantitation (BLQ) will have a value of LLOQ value divided by 2 in the computation of descriptive statistics. Mean concentration-time data will be graphically presented. Results from both the placebo-controlled treatment period and OLE will be summarized over time.

Predose samples that are missing will be assigned as missing.

Concentrations assigned a value of missing will be omitted from the calculation of descriptive statistics. If 50% or more of the values are BLQ at one scheduled time point, the arithmetic mean will be reported as BLQ.

The individual and mean plasma concentrations and the individual and mean concentrations in skeletal muscle biopsies will be presented by scheduled time point in figures on linear scales.

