Fulcrum anticipates that a 15 mg BID dosing regimen, as proposed under fed conditions for the planned phase 2 studies in FSHD, will result in mean steady-state C_{min} and C_{max} values of approximately 30 ng/mL and 75 ng/mL, respectively; the corresponding values for a 7.5 mg PO BID dosing regimen are 16 ng/mL and 38 ng/mL, respectively. Thus, the 15 mg BID regimen is expected to maintain steady-state losmapimod plasma concentrations above the optimal level of 30 ng/mL needed for robust target engagement, while the 7.5 mg PO BID dose would fall below that at predose levels. Importantly, at the proposed dose level of 15 mg PO BID, exposures in FSHD subjects are not expected to exceed those previously demonstrated to be safe in humans in multiple previous studies by GSK in healthy volunteers and various patient populations (Barbour et al, 2013; Cherian et al, 2011; Pascoe et al, 2017; Watz et al, 2014).

In Study 1821-CLP-101, similar relative bioavailability (AUC) was demonstrated between one 15-mg losmapimod tablet versus two 7.5-mg losmapimod tablets. Peak exposure (C_{max}) of losmapimod was reduced by 20% with one 15-mg tablet, although this did not have an impact on target engagement, which was consistent with prior Fulcrum studies.

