6.3. PHARMACOKINETIC AND PHARMACODYNAMIC ASSESSMENTS

6.3.1. Pharmacokinetic Assessments

During the placebo-controlled treatment period, blood samples will be collected to measure the plasma concentrations of losmapimod at Day 1 (baseline), Week 4, Week 16, and Week 36 at the

following time points: immediately predose and 4 hours (± 30 minutes) after administration of the study dose. Blood samples will also be taken, when feasible, after dosing during the Week 12, Week 24, and Week 48 visits, preferably ≥ 1 hour after dosing (Table 2). During the OLE, blood samples will be collected to measure the plasma concentration of losmapimod after dosing at the Week 144 visit, preferably ≥ 1 hour after dosing (Table 3).

For each plasma PK sample, approximately 3 mL of blood will be collected via an intravenous catheter placed in an antecubital vein in the arm into a 3 mL, lavender-capped vacutainer tube containing K2-EDTA. The indwelling catheter will be kept patent by saline flush after each blood sampling. The exact actual clock time of withdrawal of the blood sample will be recorded.

Skeletal muscle biopsies will be taken at Day 1 (baseline; predose) and at Week 16 or Week 36 to assess the losmapimod concentrations in muscle during the placebo-controlled treatment period (Table 2). Skeletal muscle biopsy procedures are described in Section 6.1.1.

Further detailed handling, processing, storage, and shipping procedures for plasma and skeletal muscle biopsy PK samples are described in laboratory manuals.

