- ^c Weight and height will be measured and BMI will be calculated once a year (ie, Week 72, Week 120, Week 168, Week 216, etc.). Weight and height will be measured with shoes off and preferably with the same balance.

- ^e Urine pregnancy tests will be performed for all female subjects of child-bearing potential before dispensation of study drug. If pregnancy is found, subjects must be terminated from the study effective immediately.
- ^f Vital signs (pulse rate, respiration rate, blood pressure, and temperature) will be collected after the subject has been seated or recumbent for at least 5 minutes and before any 12-lead ECG assessment or blood sampling is performed.
- ^g Physical examination at the safety follow-up visit includes an evaluation of body systems, including but not limited to the following: skin; head, eyes, ears, nose, and throat; respiratory system; cardiovascular system; abdomen (liver, spleen); lymph nodes; neurological system; and MSK system. Symptom-directed physical examinations can occur at any time during the study if triggered by adverse events or if deemed necessary by the investigator.
- ^h Twelve-lead ECGs will be performed after subjects have been recumbent for at least 5 minutes. Twelve-lead ECGs will be performed after the measurement of vital signs and before any procedures that may affect heart rate (eg, blood sampling).
- ⁱ Blood samples for PK will be collected after dosing at the Week 144 clinic visit only, preferably ≥ 1 hour after dosing.
- ^j The appropriate amount of study drug supply (losmapimod) will be given to the subject at each applicable visit to allow for dosing until their next scheduled study visit plus additional tablets to cover the visit window or additional study drug will be provided to the subject via a courier, as applicable. Study drug (losmapimod) will be taken twice daily and should be taken with food.
- ^k All medications taken within 28 days before screening through the safety follow-up visit will be recorded.

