#### **4.5. Visit Windows**

In general, data for assessments that are collected by scheduled visits will be mapped to visits that appear in the schedule of assessments per the protocol using the actual study day of assessment. Data mapped to scheduled visits will include all data collected up to the

reporting cut-off date and may include withdrawal visits, unscheduled visits, end of treatment, and safety follow-up visits.

Visit windows will be continuous from the midpoint between two consecutive study visits and will be dependent on the schedule of assessments for each variable independently. For analysis that includes presentation of data in the placebo-controlled treatment period, there is an exception in the Week 16 analysis window. This has been extended to allow for potentially delayed visit due to COVID-19 pandemic. An example of the Vital Signs visit window is given in [Table 4-1](#). Visit windows for each variable will be constructed in the same manner.

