- f Vital signs (pulse rate, respiration rate, blood pressure, and temperature) will be collected after the subject has been seated or recumbent for at least 5 minutes and before any 12-lead ECG assessment or blood sampling is performed.
- g Physical examination at the safety follow-up visit includes an evaluation of body systems, including but not limited to the following: skin; head, eyes, ears, nose, and throat; respiratory system; cardiovascular system; abdomen (liver, spleen); lymph nodes; neurological system; and MSK system. Symptom-directed physical examinations can occur at any time during the study if triggered by adverse events or if deemed necessary by the investigator.
- h Twelve-lead ECGs will be performed after subjects have been recumbent for at least 5 minutes. Twelve-lead ECGs will be performed after the measurement of vital signs and before any procedures that may affect heart rate (eg, blood sampling).

- i Subjects will be screened for any contraindications to MRI as per clinic standard practice.
- j The MRI at the ET visit will not be repeated if an MRI was completed during the previous 12 weeks.
- k Blood samples for PK will be collected after dosing at each clinic visit, preferably  $\geq 1$  hour after dosing.
- l [REDACTED]
- m The appropriate amount of study drug supply (losmapimod) will be given to the subject at each applicable visit to allow for dosing until their next scheduled study visit plus additional tablets to cover the visit window or additional study drug will be provided to the subject via a courier, as applicable. Study drug (losmapimod) will be administered as 2 tablets taken twice daily and should be taken with food.
- n All medications taken within 28 days before screening through the safety follow-up visit will be recorded.

**14.3. Protocol Version 5.0 Schedule of Study Procedures: Schedule of Events: Open-Label Extension (Visits Will Occur Quarterly Until 90 Days After Commercial Drug Availability Post Regulatory Approval or Study is Discontinued)**

Procedure	Week 60	Week 72	Week 84	Week 96	ET Visit a	Safety Follow-Up 7 Days After the Last Dose of Study Drug
Visit Window (days) b	±7	±7	±7	±7		±3
Weight, height, and BMI c		X				
Urine pregnancy test e	X	X	X	X	X	X
Vital signs f	X	X	X	X	X	X
Physical examination g						X
Standard 12-lead ECG h	X	X	X	X	X	X
Serum chemistry	X	X	X	X	X	X
Hematology	X	X	X	X	X	X

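### Plasma losmapimod is averaged by scheduled visit although many samples have no fixed draw time and off-drug samples are not excluded, so trends in visit means cannot be told apart from changes in draw time

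*SAP*

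**What the plan says.** **Sampling.** Protocol Section 6.3.1 fixes the Day 1 and Week 4, 16 and 36 samples at "immediately predose and 4 hours" after the dose, within 30 minutes. The other visits are looser: "Blood samples will also be taken, when feasible, after dosing during the Week 12, Week 24, and Week 48 visits", with at least 1 hour preferred. In the OLE, footnote k of the version 4.0 schedule (SAP Appendix 14.2) reads "Blood samples for PK will be collected after dosing at each clinic visit", with the same preference. Under version 5.0, footnote i of Protocol Table 3 reads "Blood samples for PK will be collected after dosing at the Week 144 clinic visit only", although the table also marks a PK sample at the ET visit. None of the untimed samples has a nominal time or a latest time.

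**Summary.** SAP Section 10 states "Losmapimod plasma and muscle concentrations will be summarized using descriptive statistics", by scheduled time point and over both study periods. Planned Figure 14.2.1 plots the mean by visit. Collection times and sampling-time deviations go to a listing. Protocol Section 7.6.5 planned the concentration figures by collection time. The SAP uses scheduled time point, and SAP Section 11 does not list the change.

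**Off-drug samples.** SAP Section 4.5 says that data mapped to scheduled visits "may include withdrawal visits, unscheduled visits, end of treatment, and safety follow-up visits". Both OLE schedules allow the ET visit to fall more than 7 days after the last dose. SAP Section 10 has no on-treatment rule and enters values below quantitation as half the LLOQ.

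**The concern.** Plasma concentration is the only OLE secondary endpoint in the protocol (Sections 2.2.2 and 7.2.2). Readers will follow its mean from visit to visit and set it against the 30 ng/mL that Protocol Section 3.2.1 ties to robust target engagement.

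When some visits have a fixed draw time and others do not, a step between visits can come from the clock alone. The same is true between two untimed visits if clinics drew earlier at one than at the other. A falling mean could then be read as lower exposure or poorer adherence. Samples taken after the drug was stopped would pull the mean in the same direction. The listing of deviations does not cure this, because no deviation can be derived where there is no nominal time.

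**Working it through.** **Inputs from the protocol.** Expected steady-state trough 30 and peak 75 ng/mL at 15 mg twice daily (Section 3.2.1). Tmax 1 to 4 h and terminal half-life about 10 h (Section 1.3). Dosing interval 12 h. Planned 38 subjects per arm.

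**Assumptions.** The documents give neither actual draw times nor the between-subject CV of exposure. Draws are taken as uniform over 1-4, 1-8 or 1-12 h after the dose, and the CV as 20% to 50%.

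**1. The plan's figure.** Doubling the stated 7.5 mg values (16 and 38 ng/mL) gives 32 and 76, close to the stated 30 and 75.

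**2. One subject, one sample.** 75/30 = 2.5-fold between peak and trough. With a 10 h half-life from a peak of 75, the 12 h value is 75 × 2^(−(12 − Tmax)/10). That is 35 ng/mL for Tmax 1 h and 43 for Tmax 4 h, a swing of 2.1- to 1.7-fold. So 2.5 is the upper figure.

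**3. Visit mean with exposure unchanged.** Steady-state one-compartment profile: C(t) ∝ e^(−kt)/(1 − e^(−12k)) − e^(−ka·t)/(1 − e^(−12ka)). The constants k and ka are solved so that the peak falls at Tmax and peak/trough = 2.5, and the curve is scaled to a peak of 75. Tmax 4 h has no solution. Mean concentration (ng/mL):

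| Tmax | Fixed 4 h ± 0.5 | 1-4 h | 1-8 h | 1-12 h | 1-4 h ÷ 1-12 h |
|---|---|---|---|---|---|
| 1 h | 59.6 | 67.7 | 57.8 | 49.8 | 1.36 |
| 2 h | 66.5 | 72.1 | 62.4 | 53.2 | 1.36 |
| 3 h | 72.8 | 71.6 | 66.1 | 56.4 | 1.27 |

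The CV due to draw time alone is 1.5-2.6% for the fixed 4 h sample, 3.5-7% for 1-4 h, 11-17% for 1-8 h and 26-28% for 1-12 h.

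**4. Sensitivity to half-life.** The fitted half-lives are 8.1, 6.9 and 5.1 h, shorter than the stated 10 h. With Tmax 1 h and a plain 10 h decline from 75, the mean over a window of w hours from the peak is 75 × (10/ln 2) × (1 − 2^(−w/10))/w. For w = 3 this is 67.7; for w = 11 it is 52.5. The ratio is 1.29, so the size hardly depends on this choice.

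**5. Draw time against exposure.** Share of single-sample variance due to draw time = CV_T² / (CV_T² + CV_B² + CV_T²·CV_B²), where T is timing and B is between-subject.

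| Draws | CV_B 20% | CV_B 30% | CV_B 50% |
|---|---|---|---|
| 1-8 h | 24-41% | 12-24% | 5-10% |
| 1-12 h | 61-64% | 41-44% | 20-22% |

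Timing exceeds half only when draws cover nearly the whole interval and CV_B is below about 27%.

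**6. Washed-out ET sample.** Three days after the last dose 2^(−72/10) = 0.0068 remains. From 30-75 ng/mL this leaves 0.2-0.5 ng/mL; at 7 days it is below 0.001. One near-zero value among 38 lowers the mean by 1/38 = 2.6%, and two lower it by 5.3%. In a group of 20, one lowers it by 1/20 = 5%. SAP Section 4.2 splits the data into four sequence and entry groups, and two of them share only 12 subjects (Protocol Section 3.1.1), so one such value weighs more there.

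**The case against.** The case for leaving the plan alone has real parts. The endpoint is descriptive, and no test or decision rule rests on these means. Adherence has its own analysis by tablet count (SAP Section 7.2.2). Collection times and individual concentrations are listed, so a careful reader can trace draw time. Untimed samples are drawn during a clinic visit, and Protocol Section 5.5 asks for the morning dose in clinic at some visits, so many draws may fall within a few hours of dosing. If draw times were distributed alike at every untimed visit, the trend among those visits would not be biased. Population PK modelling could use actual times, but it is optional and reported separately. Protocol Section 7.6.5 itself summarises its tables by time point, and its collection time could be read as nominal time. These points limit the size. They do not remove the gap, because the planned summaries themselves make no use of time since dose.

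Some stronger readings are tempting but not supported:

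- *The visit means reflect draw time more than exposure.* This needs the between-subject CV and the draw times, which the documents do not give. Over most of the assumed range exposure outweighs timing (step 5).
- *A 38% fall, from the average draw moving from 3 h to 10 h* (2^(−7/10) = 0.62). Nothing suggests an average draw at 10 h.
- *Every OLE visit is affected.* Version 4.0 sampled each OLE visit, but version 5.0 schedules Week 144 only, plus ET.
- *ET samples distort the means badly.* ET is requested as soon as possible, the PK table uses the open-label analysis set (so subjects who never entered the OLE are out), and the median is also reported.
- *The tablet change confounds exposure.* Protocol Section 3.2.1 reports a 20% lower peak with one 15-mg tablet, but also similar AUC and no impact on target engagement.

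**Conclusion.** The point holds in a limited form. The plan averages fixed and untimed samples by scheduled visit, and it has no rule that keeps off-drug samples out. A change in the visit mean therefore cannot be attributed to exposure without knowing when the blood was drawn. With unchanged exposure, the possible drift between visits is about 1.27- to 1.36-fold if draws cluster at 1-4 h at one visit and spread over 1-12 h at another, and smaller for narrower differences. These sizes rest on assumed draw windows and a simple profile fitted to the protocol's expected trough and peak. The off-drug effect is a few percent of a visit mean per sample in the larger groups. Because the endpoint is descriptive, this is a minor-to-moderate improvement and no threat to the study's conclusions.

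**What to change.** Amend SAP Section 10 and record the change in SAP Section 11:

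1. Leave samples drawn more than one dosing interval after the last dose, including those at ET and after treatment discontinuation, out of the on-treatment means, and list them. State a small tolerance, since the fixed predose samples sit about one interval after a dose by design.
2. Keep by-scheduled-time summaries for the fixed predose and 4-hour samples.
3. For untimed samples, plot individual concentrations against actual time since last dose where the dose time is recorded, which fits Protocol Section 7.6.5. Add a summary in a few broad time-since-dose bins, pooled across entry groups. Keep samples without a dose time in a separately labelled by-visit summary, so that OLE data are not lost.
4. Mark tablet form in the listing and figure. Do not cross-classify by it.

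**Cost.** SAP wording and some extra programming. Draw clock times are already recorded (Protocol Section 6.3.1), and last-dose dates are already needed for exposure (SAP Section 7.2.1). The main limit is dose times in the OLE: diaries cover at most part of the placebo-controlled period (Protocol Section 5.7), so some samples cannot be placed on the time axis. Bins will have small cells, which is the reason for pooling and for few cut-points.
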